7.1.3. Lenalidomide Dosing Scheme

All subjects will receive lenalidomide and self-administer a starting dose of 25 mg oral lenalidomide daily on Days 1 to 21 of each cycle. No more than 21 doses of lenalidomide will be dispensed per cycle. Investigators will follow the package insert or SmPC ([Revlimid[®] PI, 2021](#); [Revlimid[®] SmPC, 2022](#)) for recommended medications for venous thromboembolic event prophylaxis and dosing modifications. It is recommended that subjects take lenalidomide in the evening about the same time each day, with or without food. Advise subjects to swallow lenalidomide capsules whole with water and not to open, break, or chew them. Treatment with lenalidomide may be modified in a deescalating fashion or discontinued based upon clinical and laboratory findings. Detailed dose modification guidelines to manage hematologic and/or other toxicities are provided in the relevant sections of the protocol.

In the event of the discontinuation of lenalidomide, in the absence of disease progression, and if the subject is still receiving benefit from the study treatment, subjects may continue with the other study treatment(s).

7.2. Concomitant Medications

All medications (including over-the-counter-medications and herbals) and blood products that are administered 21 days prior to start of treatment (Day –8) and throughout subject's participation in the study until the 90-day post-treatment follow-up visit must be recorded in the source document and on the eCRF, including date, time, and dose of administration. Concomitant medications for other medical conditions are permitted as clinically indicated, subject to specific requirements outlined below.

Subjects may not concurrently receive:

- Other experimental therapeutics for their malignancy
- Live viral vaccine within 30 days of Day –8, during treatment, within 60 days of the last dose of plamotamab, or within 90 days of the last dose of tafasitamab

Subjects may receive the following concurrent therapy:

- Antiemetics, antidiarrheals, anticholinergics, antispasmodics, antipyretics, antihistamines, analgesics, antibiotics, and other medications intended to treat symptoms
- Prophylactic filgrastim may **NOT** be administered after the first dose but may be administered during subsequent dosing in subjects who experience Grade 3 or 4 neutropenia as per the American Society of Clinical Oncology guidelines ([Robinson, 2018](#)). If a subject develops neutropenia after the first dose, they may be treated with filgrastim after the second or subsequent dose.
- Subjects who experience CRS should receive aggressive intervention and supportive measures. These may include, but are not limited to, acetaminophen, antihistamines, corticosteroids, IV fluids, bronchodilators, epinephrine, vasopressors, oxygen, and tocilizumab (see [Section 4.6](#) for guidance on management).
- Transfusions such as red blood cells (RBCs) and platelets are permitted if medically indicated. These should be leukocyte-filtered and irradiated to prevent development of transfusion-associated, graft-versus-host disease. All attempts should be made to avoid blood product transfusions on the same day as study drug administration.
- Subjects who experience indigestion, nausea, and/or vomiting may be treated with histamine receptor, type 2 antagonists, or proton pump inhibitors
- Subjects may take vitamins and/or supplements provided they are documented on the medication eCRF
- Subjects may have received hepatitis B reactivation prophylaxis with entecavir, tenofovir, or lamivudine

7.3. Treatment Compliance

The Sponsor or its designee will monitor the study according to ICH GCP guidelines. All intravenous investigational therapy will be prepared and administered at the study site, and complete records of administration doses, times, durations, and supportive therapies will be kept. Lenalidomide for oral use will be provided via a specialty pharmacy in the US or as clinical trial material/investigational medicinal product. An accurate accounting of the dispensing and return of lenalidomide for each study subject will be maintained in source documents or pharmacy drug accountability logs on an ongoing basis by a member of the study site staff. Additionally, if any IMP is lost or damaged or if the study subject misses a dose, this information should be documented in the study subject's EDC and source documents. Subjects will be asked to complete a diary of lenalidomide administration to document compliance with therapy.

7.4. Treatment Assignment, Randomization, and Blinding

Prior to administration of any study therapy, each subject must have completed all screening activities, and the Medical Monitor or designee must review the screening data and provide approval for the subject to start treatment in Part 1 or be randomized into Part 2. All subjects that

sign an informed consent form (ICF), including screen failures, will be entered into the electronic data capture (EDC) system.

In Part 1, subjects will be considered enrolled if they have signed the ICF, if the Medical Monitor or designee has confirmed the eligibility of the subject for entry, and if they have received the Day – 8 tafasitamab priming dose. Treatment assignment and Study Subject Number assignment will be done by a Randomization and Trial Supply Management (RTSM/IRT) system.

In Part 2, subjects that have signed the ICF and have eligibility confirmed by the Medical Monitor or designee may be randomized. The initiation of study treatment will occur within 72 hours of randomization. Randomized subjects will start with tafasitamab priming doses on Day –8 and –4. Subjects will be randomized at a 1:1 ratio to the 2 treatment arms, stratified by IPI risk score at baseline (3 to 5 versus 0 to 2), number of lines of prior therapy (1 versus ≥ 2), and primary refractory (yes versus no). A maximum of 36 primary refractory subjects may be enrolled. No blinding is specified due to the potential of CRS with plamotamab and infusion-related reactions with tafasitamab. Randomization is performed by a designated member of the Investigator's staff once the Sponsor has reviewed the eligibility. Treatment assignment and Study Subject Number will be assigned by an RTSM/IRT system. Instructions for registering subjects for treatment and performing randomization will be provided in a separate user's manual.

7.5. Pretreatment Evaluations

Only those subjects who meet all inclusion but no exclusion criteria specified in [Section 6](#) may be enrolled into this study. Prior to the initiation of any on-study testing, including screening testing, the subject must have signed the ICF and received a Subject Screening Number (see [Section 7.4](#)) from the EDC system. The pretreatment period lasts for up to 28 days and includes screening evaluations (up to 28 days before the first dose of study drug) and baseline assessments.

See [Table 9](#) for the Schedule of Assessments and [Table 10](#) (plamotamab) for ADAs, cytokines, PK, ECGs, and rituximab levels, and see [Table 11](#) (tafasitamab) for the sampling days for ADA and PK levels.

7.5.1. Screening Evaluations (Up to Day –35)

In Part 1, screening assessments are to be performed during the 28-day window prior to the priming dose of tafasitamab. In Part 2, screening assessments are to be performed within 28 days of randomization.

- Obtain signed informed consent (may be done up to Day –35)
- Review inclusion and exclusion criteria
- Medical history and physical exam (PE)
- Neurologic examination will be assessed using the ASTCT ICANS Consensus Grading for Adults (see [Section 4.6.1.7](#))

- Any cytogenetic information available on the tumor from time of original diagnosis and at transformation (if applicable) should be recorded, including cytogenetics, fluorescent in situ hybridization (FISH) analysis, and sequencing data
- Vital signs (supine or sitting position, including heart rate, blood pressure, temperature, respiratory rate, and blood oxygen saturation by pulse oximetry)
- Height, weight
- ECOG performance status (see [Appendix A](#), Performance Status Scale)
- Electrocardiogram (ECG), standard 12-lead, supine position
- Complete blood count (CBC): RBC, hemoglobin, hematocrit, mean corpuscular volume (MCV), RBC distribution width (RDW), white blood cell (WBC) with differential (neutrophils, lymphocytes, monocytes, eosinophils, basophils, myelocytes, promyelocytes; include percent and absolute, if reported) and platelet count
- Chemistry panel (sodium, chloride, potassium, bicarbonate, blood urea nitrogen, creatinine, glucose, uric acid, calcium, phosphorous, total bilirubin, ALT, AST, total protein, albumin, alkaline phosphatase, LDH, as well as serum gamma-glutamyl transferase [GGT], amylase, lipase, ferritin (screening only), and C-reactive protein (screening only))
- Coagulation panel (prothrombin time [PT]/international normalized ratio [INR] and activated partial thromboplastin time [APTT])
- Urinalysis with microscopy (pH, specific gravity, ketones, leukocyte esterase, bilirubin, blood, and protein; microscopy may include RBCs, WBCs, hyaline casts, RBC casts, WBC casts, granular casts, waxy casts [include microscopy findings in EDC only if reported])
- Hepatitis B (HBsAg, HBcAb, and HBsAb) and C (HCV), and HIV screening. These tests may have been performed within the previous 8 weeks.
- If HBcAb or HBsAg is positive, perform hepatitis B DNA testing. If subject is negative, subject may be enrolled if hepatitis B reactivation prophylaxis is initiated with entecavir, tenofovir, or lamivudine
- SARS-CoV-2 nucleic acid or antigen test (to be completed within 7 days prior to Day – 8)
- Urine or serum β -hCG pregnancy test for women of childbearing potential performed at screening (within 10 to 14 days of Day –8) and at Day –8 or an FSH test for postmenopausal women. An FSH test only needs to be performed once during screening to confirm that the subject is not capable of becoming pregnant.

- Lenalidomide Counseling is performed during screening prior to Day –8. Please see the supplemental Summary of Pregnancy Prevention Strategies, provided under separate cover, for details.
- The following are to be sent to the central laboratory per the laboratory manual:
 - Peripheral blood for T-, B-, and NK cells (TBNK); leukocyte flow cytometry to assess frequencies of circulating leukocytes; and for leukocyte phenotyping, function, and activation markers
 - Peripheral blood for ctDNA analysis to assess MRD (see [Section 8.2.1](#))
 - Archival blocks (preferred) or unstained slides for cell of origin determination by a central pathologist (see [Section 8.2.2.1](#))
 - Biopsy of disease site. Subjects will be consented and may undergo an optional (recommended) biopsy to obtain fresh tumor tissue (for those subjects with accessible superficial lymphadenopathy that can easily and safely be accessed) (see [Section 8.2.2.1](#) and [Section 8.2.2.2](#)).
- Tumor assessments will be performed by the Investigator using PET/CT or CT scans and bone marrow if bone marrow involvement is suspected or known. The same evaluations (ie, imaging, blood, bone marrow) performed at baseline will be performed at each subsequent disease assessment. All tumor assessments should be performed within 21 days prior to the first dose of Study Drug (Day –8). Tumor assessments must be read locally, and scans and other relevant information must be submitted to the central imaging designee for review by the BIRC. Redacted tumor assessments including, but not limited to, assessment reports and/or actual data (Digital Imaging and Communications in Medicine [DICOM] files) for scans, blood analysis, and bone marrow biopsy pathology reports may be requested by the Sponsor. If requested by the BIRC, additional information may be required, including the interpretation, differential, and addenda when available (flow cytometry, cytogenetics, FISH, and/or molecular testing.)
- Record AEs and concomitant medications
- During Part 1 and 2, registering a subject for approval by Sponsor and during Part 2, randomization on Day –10/–9 via third party RTSM/ IRT system by a designated member of the Investigator’s staff once all eligibility criteria have been verified

7.5.2. Day –8, Day –4, and Day –1

- Abbreviated PE (Day –8 and Day –1 only)
- Neurologic examination will be assessed using the ASTCT ICANS Consensus Grading for Adults (Day –1 only, see [Section 4.6.1.7](#))

- Vital signs (supine or sitting position, including heart rate, blood pressure, temperature, respiratory rate, and blood oxygen saturation by continuous pulse oximetry)
- Weight (Day –8 and Day –1)
- ECOG performance status (see [Appendix A](#))
- CBC with differential (percent and absolute) and platelet count (see [Section 7.5.1](#)) (Day –8 and Day –1 only)
- Chemistry panel (see [Section 7.5.1](#)) (Day –8 and Day –1 only)
- Fibrinogen (Day –1 only)
- Coagulation panel (PT/ INR and APTT) (Day –1 only)
- Urinalysis (see [Section 7.5.1](#)) (Day –8 and Day –1 only)
- Urine or serum β -hCG pregnancy test for women of childbearing potential (Day –8 and Day -1 only)
- The following to be sent to the central laboratory per the laboratory manual:
 - Serum sample for rituximab level (Day –1 only)
 - Serum samples for tafasitamab PK and ADA (Day –8 only)
 - Peripheral blood for TBNK, leukocyte flow cytometry (Day –8 only)
 - Peripheral blood for RNA analysis (Day –8 only, prior to tafasitamab dose)
- Administration of tafasitamab on Day –8 and Day –4
- Record concomitant medications and AEs

7.6. Treatment Evaluations

7.6.1. Treatment Cycles

The schedule of required procedures and clinical site study days for each cycle is detailed in [Table 9](#), [Table 10](#), and [Table 11](#). The day prior to C1D1 is Day -1. Subjects in Part 1 and subjects randomized into Arm A of Part 2 will be admitted to an inpatient facility and monitored for a minimum of 72 hours following dosing for the first dose of plamotamab and for 24 hours following any subsequent dose escalation.

After discontinuation of treatment, subjects will be followed for PFS and OS every 2 months by telephone, email, or mail contact by the site up to 5 years or until death.

Study days for required procedures are specified in the Schedule of Assessments (Table 9). The procedures include the following:

Clinical Assessments: Clinical assessments include the following:

- Abbreviated (study-related) medical history
- PE, including weight and tumor assessment (examination of skin, head, eyes, ears, neck, and throat [HEENT], bidimensional measurement of cervical, supraclavicular, axillary, and inguinal lymph nodes, spleen size [below costal margin], heart, chest, lungs, abdomen, extremities, neurologic, and back).
- Neurologic examination will be assessed using the ASTCT ICANS Consensus Grading for Adults (see Section 4.6.1.7)
- Vital signs (supine or sitting position, including blood pressure, heart rate, respirations, temperature, and blood oxygen saturation by continuous pulse oximetry)
 - For tafasitamab infusion, vital signs and clinical assessment for AEs are monitored during and after the end of the infusion. Timepoints include the following: predose and 30 (\pm 5) minutes after end of infusion (EOI).
 - For plamotamab infusion, vital signs and clinical assessment for AEs are monitored for a minimum of 5 hours after the end of the infusion. Timepoints include: predose; approximately 15, 30, and 60 minutes after start of plamotamab infusion (\pm 5 minutes); at end of infusion (\pm 5 minutes); approximately 15 (\pm 5) minutes; 30 (\pm 5) minutes; 60 (\pm 10) minutes after EOI; and then hourly for 4 additional hours (all windows \pm 15 minutes). The pulse oximetry for blood oxygen saturation level needs to be recorded with each vital sign collection; however, pulse oximetry monitoring must be maintained continuously, as practical, throughout the entire admission period for each administration of plamotamab, regardless of inpatient or outpatient status. For subjects who tolerate 4 consecutive infusions of plamotamab at a stable dose and schedule without CRS or an infusion reaction during the infusion or post-infusion observation period, the post-infusion observation period and vital signs assessment may be reduced from 5 hours to 2 hours.
- ECOG performance status (see Appendix A, Performance Status Scale).
- Supine ECG, standard 12-lead (see the Schedule of Assessments [Table 9] for timing of collections, and as clinically indicated). Triplicate ECG at C1D1 only, prior to the Plamotamab infusion. All ECG tracings will be submitted electronically to the Sponsor either by file transfer or scanning the original tracing. Additional details will be provided in a separate manual.
- Lenalidomide Counseling is performed on Day 1 of each cycle. Please see the supplemental Summary of Pregnancy Prevention Strategies, provided under separate cover, for details.

- Record concomitant medications
- Record AEs (CTCAE and CRS revised grading system)
- Tumor assessments will be performed as outlined in [Section 9](#) after Cycle 2, then at the end of even-numbered cycles up to Cycle 12, then every 3 cycles up to Cycle 36, and then every 4 cycles up to Cycle 60, and at EOT.

Laboratory Assessments: Safety laboratory assessments, including CBC with differential, chemistry panel, fibrinogen, coagulation panel, urinalysis, and pregnancy tests, may be completed up to 24 hours prior to the visit day. Excepted is the pregnancy test prior to the first dose of lenalidomide, which should be completed on Cycle 1 Day 1, within 24 hours of initiating treatment. Safety laboratory values, except for differential counts, fibrinogen, coagulation panel, and urinalysis, should be reviewed before starting study drug infusion.

- CBC with differential (absolute and percent), platelet count, and blast count, if reported (see [Section 7.5.1](#))
- Chemistry panel (see [Section 7.5.1](#))
- Fibrinogen
- If HBcAb serology is positive, HBsAg and hepatitis B DNA testing should be performed, with results available prior to dosing, on Day 1 of Cycles 2 and later, and at EOT (unless HBsAb is also present).
- Coagulation panel (prothrombin time PT/INR and APTT)
- Urinalysis (see [Section 7.5.1](#))
- Urine or serum β -hCG pregnancy test for women of childbearing potential should occur weekly during the first 4 weeks of lenalidomide, then on Day 1 of each subsequent cycles for dosing of plamotamab, tafasitamab, or lenalidomide. If menstrual cycles are irregular, the pregnancy testing should occur every 2 weeks during each subsequent cycle.
- The following are to be sent to the central laboratory per the laboratory manual:
 - Serum samples for plamotamab and tafasitamab ADA, cytokines, and plamotamab and tafasitamab PK (see [Table 10](#) and [Table 11](#) for collection schedule). All samples should be drawn within the window indicated on [Table 9](#) and of the designated time and should be labeled with the exact, actual time of sampling.
 - Peripheral blood for TBNK, leukocyte flow cytometry
 - Peripheral blood for RNA analysis

- Peripheral blood for ctDNA analysis
- Tumor biopsies (for those subjects who provided consent) collected once at follow-up (See [Section 8.2.2](#) and [Table 9](#))

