		
on the C1D1 dose, in which case 100% of the previous dose may be given.
 
 • For subsequent plamotamab infusions, if: 
 – Toxicity does not recur or recurs at a Grade 1 severity, escalate to full dose of plamotamab at the time of the next dose. – Toxicity recurs at a Grade 2 severity, maintain 75% dosing of plamotamab. – Toxicity recurs at \geq Grade 3 severity at any time or if a Grade 2 takes more than 10 days to resolve to \leq Grade 1, discontinue plamotamab permanently. • Lenalidomide is also modified if a \geq Grade 3 CRS event occurs: 
 – During the first 5 doses of plamotamab: Reduce current dose of lenalidomide by 10 mg (or to 5 mg if currently at 10 mg) for subsequent doses until C4D1, when lenalidomide may be increased back to the dose prior to CRS. If CRS recurs at \geq Grade 2 on subsequent reduced dose lenalidomide, permanently discontinue lenalidomide. – After the first 5 doses of plamotamab: Reduce lenalidomide by 10 mg (or to 5 mg if currently at 10 mg) for all subsequent doses. If CRS recurs at \geq Grade 2 on subsequent reduced dose lenalidomide, permanently discontinue lenalidomide. • Tafasitamab dose is not modified.
Myelosuppression	Platelet count of less than 50,000/ μ L	
 • Withhold plamotamab, tafasitamab, and lenalidomide and monitor CBC weekly until platelet count is 50,000/μL or higher. • Resume plamotamab and tafasitamab at the same dose and lenalidomide at a reduced dose. Refer to lenalidomide prescribing information for dosage modifications. • If recurrence, repeat drug withholding and lenalidomide reduction steps until minimal lenalidomide dose is reached per lenalidomide prescribing information. • If recurrence at minimal lenalidomide dose, repeat drug withholding step (first bullet above) then reduce the next scheduled plamotamab dose to 75% of the previous dose.

Adverse Reaction	Severity	Dosage Modification

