- ^q PET/CT and bone marrow biopsy/aspirate (for subjects with known bone marrow involvement). All studies for the baseline assessment should be performed within 21 days prior to Day -8. After Cycle 12, perform disease assessments every 3 cycles (or Q12 weeks) up to Cycle 36 and every 4 cycles (Q16 weeks) up to Cycle 60. Any unscheduled disease assessment performed in suspicion of progressive disease must be recorded in the eCRF.
- ^r PHI-redacted tumor assessments including, but not limited to assessment reports and/or digital imaging files (DICOM) for scans/imaging, blood, and bone marrow biopsy pathology reports are to be provided to support response assessments.
- ^s Archival tissue from excisional biopsies of lymph node to be sent to the designated central laboratory as an archival block (**preferred**) or up to 43, if possible, unstained slides. Archival tissue must predate study treatment. If archival tissue is not available or is insufficient, the screening fresh tumor biopsy becomes mandatory to satisfy the inclusion criterion.
- ^t Fresh tumor biopsy will be collected at screening up to 21 days prior to Day -8. The on treatment fresh tumor biopsy performed after the fourth dose between the C1D22 and C2D1 visit. Fresh tumor biopsy is strongly encouraged but is optional and requires separate consent. The baseline sample becomes mandatory for study participation if archival tissue is not available to satisfy the inclusion criterion.
- ^u The Screening (baseline) sample will come from the submitted archival or fresh tumor biopsy sample to identify malignant clones. Samples of whole blood and plasma will be collected through C2D1; only whole blood will be collected at C2D26, C6D1, C9D1, C12D1 and EOT for the detection and quantification of ID clonotype(s) that were identified from the baseline sample.

- ^v Male subjects will be followed for 6 months, and female subjects 8 months following the last dose of study drug to confirm contraceptive use.
- ^w Subjects who complete a tumor assessment within the prior 14 days do not have to repeat the EOT tumor assessment. If a subject was removed from study for disease progression and this response data for that applicable visit is adequately documented in EDC, the post-treatment (EOT and 90 days post EOT) tumor assessments do not need to be repeated.
- ^x Treatment-related SAEs should be followed up until resolution.

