11.3. Sample Size and Power

11.3.1. Progression-Free Survival

PFS as assessed by the BIRC is the primary endpoint for Part 2 of this study. For determination of the sample size, it is assumed that triple combination treatment could improve the median PFS from 12 months (under treatment with tafasitamab + lenalidomide (Duell, 2021) to 23.5 months under the triple combination treatment (plamotamab + tafasitamab + lenalidomide), corresponding to a hazard ratio (HR) of 0.51 with all randomized subjects (it is estimated that 90% of subjects will be central pathologically confirmed as DLBCL).

The log rank test has 90% power with the sample size of 200 (93 events) to preserve the type-I error of 0.025 (one-sided). A loss to follow-up rate of 1.5%/month was assumed for sample size calculations.

Subjects will be randomized 1:1, stratified by IPI risk score at baseline (3 to 5 versus 0 to 2), number of lines of prior therapy (1 versus ≥ 2), and primary refractory (yes versus no). A maximum of 36 primary refractory subjects may be enrolled into the sample size of 200.

Enrollment of 200 subjects is estimated to require 27 months with minimum follow-up time of 6 months. The primary efficacy analysis will occur when 93 PFS events per independent review have been observed. Efficacy boundaries and estimated timing for the analysis is displayed in [Table 21](#).

Table 21: Efficacy Boundaries and Properties for Progression-Free Survival Analyses

Analysis	Value	Efficacy
Final	Z	1.9600
N: 200	p (1-sided)	0.0250
Events: 93	HR at bound	0.6659
Month: 33	P(Cross) if HR = 1	0.0250
	P(Cross) if HR = 0.51	0.9000

p (1-sided) is the nominal α for testing.

HR at bound is the approximate HR required to reach an efficacy bound

P(Cross if HR = 1) is the probability of crossing a bound under the null hypothesis

P(Cross if HR = 0.5) is the probability of crossing a bound under the alternative hypothesis

HR = hazard ratio.

An interim analysis for OS at the time of final PFS analysis will be implemented using the group sequential design in addition to the final OS analysis. [Table 22](#) provides the timing of PFS and OS analysis.

Table 22: Summary of Interim and Final Analyses Strategy

Analyses	Key Endpoints	Timing	Estimated Time after First Subject Randomized	Primary Purpose of Analysis

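### Tumour assessments follow treatment cycles, not weeks from randomization, and the protocol does not say whether a dose hold moves them; if holds shift cycles more in Arm A, PFS is slightly biased in its favour

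*Protocol*

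**What the plan says.** **Assessment schedule.** Protocol Section 7.6.1 sets tumour assessments after Cycle 2, "then at the end of even-numbered cycles up to Cycle 12", then every 3 cycles to Cycle 36 and every 4 cycles to Cycle 60. Table 9 puts the early ones on Day 26 ± 3 of Cycles 2, 4, 6 and later even cycles. Footnote q of that table introduces weeks only after Cycle 12: "perform disease assessments every 3 cycles (or Q12 weeks) up to Cycle 36", and later every 4 cycles with 16 weeks as the equivalent. Neither place counts from randomization.

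**Endpoint.** The primary endpoint for Part 2 is PFS by blinded independent review, timed from randomization (Sections 4.2.1 and 11.2).

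**Holds.** For a low platelet count, Table 8 in Section 4.7 instructs: "Withhold plamotamab, tafasitamab, and lenalidomide and monitor CBC weekly until platelet count" has recovered. The neutropenia and febrile neutropenia rows also stop all three drugs. Sections 4.6.3 and 4.6.3.1 say that falls in neutrophils and platelets may become worse or last longer in combination, and that dosing may be delayed.

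**What is not said.** Section 4.7 counts a dose held for 7 days or more (weekly dosing) or 14 days or more (two-weekly dosing) as missed. It does not say whether the cycle count, and with it the assessment, then moves. Section 7.6.4 continues efficacy assessments after discontinuation for toxicity without progression, but gives no interval.

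**The concern.** Progression is dated at the assessment that shows it, so the schedule is part of the endpoint. If a hold pushes back the next cycle, a cycle-based assessment moves with it. A third myelosuppressive drug could make such shifts more frequent in Arm A. Later assessments in one arm lengthen that arm's observed PFS without any benefit. The trial is open-label, so after Cycle 12 sites that know the arm would choose between cycles and weeks once the two diverge.

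There is also a definitional cost. The estimand in Section 11.2 lists missing two or more tumour assessments as an intercurrent event. If due dates float with cycles, it is unclear when an assessment has been missed.

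**Working it through.** **1. The plan's own figures.** Section 11.3.1 states: "The log rank test has 90% power with the sample size of 200 (93 events) to preserve the type-I error of 0.025 (one-sided"). The effect is medians of 12 and 23.5 months, "corresponding to a hazard ratio (HR) of 0.51 with all randomized subjects"; 12/23.5 = 0.511. Allocation is 1:1.

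- Events (Schoenfeld): 4 × (1.960 + 1.282)² / (ln 0.51)² = 42.03 / 0.4534 = 92.7, so 93. Power with 93 events is 90.1%.
- Hazard ratio at the bound: exp(−1.96 × 2/√93) = 0.666 (stated 0.6659).
- Expected events at month 33, with 27 months' uniform accrual, 6 months' minimum follow-up and 1.5% monthly loss: 93.7.

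The design figures reproduce. (Section 4.1.2 gives 89 events for the same analysis; 93 is used here.)

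**2. Scale of the delay.** If progression falls evenly between assessments, the mean lag is half the interval: 56/2 = 28 days on an 8-week schedule. Stretching 28-day cycles to 29.4, 31.5 or 35 days (5%, 12.5%, 25%) makes the interval 58.8, 63 or 70 days. The extra lag is then 1.4, 3.5 or 7 days. The simulation below gives 1.3, 3.4 and 6.6 days.

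**3. Effect on the test.** The main simulation uses 200 subjects, exponential PFS, the accrual and loss above, assessments on the Table 9 schedule with ± 3 days' scatter, an unstratified log-rank test at the 93rd detected event, and 6,000 trials with no true effect (Monte Carlo error about 0.2 points). The following assumptions are not in the documents: 15% of events are deaths without prior progression; a hold moves all later assessments; a single hold falls in Cycles 1 to 6; extra holds occur only in Arm A.

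| Arm A scenario | Null HR | One-sided error |
|---|---|---|
| Same schedule as Arm B | 0.997 | 2.6% |
| One hold of 1–4 weeks in 25% of subjects | 0.990–0.993 | 2.6–2.8% |
| One hold of 1–4 weeks in 50% | 0.982–0.989 | 2.8–3.0% |
| One hold of 2–4 weeks in all | 0.973–0.982 | 3.1–3.3% |
| Every cycle 5–25% longer | 0.972–0.982 | 3.2–3.4% |

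Two further sets of null simulations bear on the extremes:

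- 20,000 trials per setting with 20% deaths: 2.5% with equal schedules; 3.3%, 3.2% and 3.6% for cycles 5%, 12.5% and 25% longer.
- 8,000 trials per setting: 3.1–3.5% for stretched cycles and 2.4–2.7% for a single hold in 25–50% of Arm A, against 2.7% with equal schedules.

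Inflation is therefore clear for systematic stretching and not distinguishable from nominal for occasional holds. It is not proportional to the delay. The likely reason is that assessment dates cluster, so a shift of a few days is enough to place Arm A's events after Arm B's at the same visit.

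**4. At the design effect** (3,000 trials): equal schedules give HR 0.507 and power 90.0%. Across the scenarios above, HR is 0.498–0.506 and power 90.0–91.1%.

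**The case against.** The strongest objection is that the documents never say a hold moves a cycle. Cycles are 28 days, visit windows are narrow, and the missed-dose rule in Section 4.7 can be read as skipping the dose while the calendar runs on. That stands: the delay is possible, not established.

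The difference between arms is also uncertain. Arm B is referred to the same Section 4.7 rules for haematologic toxicity, so only excess holds in Arm A matter. Several plamotamab toxicities (Grade 2 CRS, Grade 3 neurotoxicity, Grade 3 liver abnormalities) leave tafasitamab and lenalidomide dosing unchanged. The protocol says cytopenias may worsen, not that they will.

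Unscheduled assessments on suspicion of progression and end-of-treatment assessments shorten the lag in both arms. The simulations include neither, so they may overstate the effect.

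A reader might infer that the schedule does delay Arm A's assessments, or that it could produce a false positive PFS result. The documents support neither. The first needs a rule that is not written. The second needs a bias far larger than any simulated, since the bound is a hazard ratio of 0.666.

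What remains is that nothing keeps assessments on the calendar during a hold, and every simulated scenario moved the null hazard ratio in Arm A's favour.

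**Conclusion.** The schedule leaves an avoidable, one-directional source of bias on the primary endpoint. It is small: a null hazard ratio of about 0.97 to 0.99 and a one-sided error of about 2.5% to 3.5%, with the upper end reached only if every Arm A cycle is stretched. At the design effect the hazard ratio moves by about 0.01, power is unaffected, and the 93-event requirement does not change. These sizes rest on holds shifting the assessment and on excess holds in Arm A, neither of which the documents establish.

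This is a cheap improvement, not a flaw that undermines the design. The SAP (Sections 1, 4.1 and 7) records termination after 3 subjects with no efficacy analyses, so it concerns the design as written and changes no reported result.

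**What to change.** In Section 7.6.1, Table 9 and footnote q, count assessments in weeks from randomization at the existing nominal intervals: every 8 weeks to week 48, every 12 weeks to week 144, then every 16 weeks to week 240. Use the same windows in both arms, regardless of dose holds or cycle delays. Remove the choice between cycles and weeks. Apply the same calendar to the assessments that Section 7.6.4 already requires after discontinuation for toxicity without progression.

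On treatment the number is unchanged: 6 + 8 + 6 = 20 scheduled assessments, as in the cycle version. With randomization on Day −10 or −9, Cycle 2 Day 26 falls 63 or 62 days later, so a week-8 assessment (day 56) comes about a week earlier than now, equally in both arms.

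The costs are that some scans fall off dosing visits and that fixed off-treatment intervals may add a few. No dosing rule changes. The protocol revision that Section 4.1.2 requires before Part 2 would have been the natural place for this.
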